**Table E5. Indications for new renal replacement therapy.**

Indication, No. (%)	Saline (n = )	Balanced (n = )	P Value
Oliguria	--	--	--
Hyperkalemia with serum potassium > 6.5 mEq/L	--	--	--
Acidemia with pH < 7.20	--	--	--
Blood urea nitrogen > 70 mg/dL	--	--	--
Serum creatinine > 3.39 mg/dL	--	--	--
Organ edema	--	--	--
Other renal failure–related indication	--	--	--
Other non–renal failure–related indication	--	--	--

## Appendix 2: Definitions of Study Variables

### **Fluids**

**Intravenous fluid** – For the SMART study, intravenous fluid will be defined as the intravenous administration of any formulation of any volume at any rate of 0.9% sodium chloride, Lactated Ringer's, Plasma-Lyte A®; 0.45% sodium chloride, 0.225% sodium chloride, dextrose in water, 20% or 5% human albumin solution, gelatins, dextrans, or hydroxyethyl starches. This will include fluid given as a bolus, fluid given as maintenance infusions, fluid given as flushes, fluid given as 'piggy-back' infusions for IV medications, fluid given through pressure-bag systems, fluid given as a part of thermodilution of pulmonary artery catheters, and fluid given to maintain the patency of peripheral venous access. This will not include carrier fluid for medications and oral fluids.

**Isotonic crystalloid** – For the SMART study, the term isotonic crystalloid will be used to refer to any of 0.9% sodium chloride, Lactated Ringer's, or Plasma-Lyte A®. Use of the term isotonic crystalloid is intended to distinguish these three fluids from colloid solutions and from significantly hypotonic (0.45% sodium chloride) or hypertonic (3% sodium chloride) crystalloid solutions, rather than to imply that the tonicities of 0.9% sodium chloride, Lactated Ringer's, or Plasma-Lyte A® are precisely comparable to extracellular fluid.

**Saline** – Saline will refer to 0.9% sodium chloride.

**Balanced Crystalloid** – For the SMART study, Lactated Ringer's or Plasma-Lyte A® will be referred to as balanced crystalloids.

### **Renal Function**

**Baseline serum creatinine** – The value for baseline serum creatinine will be determined in a hierarchical approach. The lowest serum creatinine between 12 months

and 24 h prior to hospital admission will be used when available. If no such creatinine value is available, the lowest creatinine value between 24 h prior to hospital admission and the time of ICU admission will be used. If no creatinine value is available between 12 months prior to hospital admission and the time of ICU admission, a baseline creatinine value will be estimated using a previously-described three-variable formula [creatinine = 0.74 – 0.2 (if female) + 0.08 (if African American) + 0.003 × age (in years)][25].

**Acute kidney injury, stage II or greater** – Stage II or greater acute kidney injury will be defined according to Kidney Disease Improving Global Outcomes (KDIGO) creatinine criteria[26] as a creatinine value between enrollment and the first of hospital discharge or 30 days at least 200% of the baseline value OR both (1) greater than 4.0 mg/dL and (2) increased at least 0.3 mg/dL from baseline. Patients may have acute kidney injury present at the time of first creatinine measurement after enrollment (prevalent AKI) or acute kidney injury developing during the study (incident AKI). Incident AKI will be defined as any creatinine value between enrollment and discharge or 30 days that is (1) increased at least 0.3 mg/dL from a preceding post-enrollment value AND (2) at least 200% of the baseline value, at least 200% of a preceding post-enrollment value, or at least 4.0 mg/dL.

**Chronic kidney disease stage III or greater** – Chronic kidney disease stage III or greater will be defined as a glomerular filtration rate less than 60 ml/min per 1.73 m^2 as calculated by the Chronic Kidney Disease Epidemiology (CKD-EPI) Collaboration equation[33] using the patient's baseline creatinine value.

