## **8.4 Data Collection**

### **8.4.1 Data at Enrollment**

1. Study Enrollment Data:
  - a. Encounter Number ("Study ID")
  - b. Medical Record Number
  - c. Date and Time of ICU Admission ("Time Zero")
  - d. Study ICU at enrollment (Medical/Cardiac/Neuro/Trauma/Surgical)

Principal Investigators: [name], [name]

Version Date: 6/15/17

Study Title: Isotonic Solutions and Major Adverse Renal Events Trial (SMART)

Institution/Hospital: Vanderbilt University Medical Center

2. Demographic Data:

- a. Age (years)
- b. Gender (male/female)
- c. Race (White/Black/Asian/Alaskan/PacificIsland/Other)
- d. Ethnicity (Hispanic, Non-hispanic)
- e. Height (cm)
- f. Weight (kg)
- g. Date and time of Hospital Admission
- h. Source of admission to ICU (ED/OR/outside hospital transfer/hospital ward/outpatient/another ICU within the hospital)
- i. Admitting service
- j. ICD-9 and ICD-10 diagnoses

3. Comorbidities:

- a. Exlihauser comorbidities
- b. CKD stage III or greater by CKD-EPI criteria
- c. Prior receipt of renal replacement therapy
- d. Predicted risk of in-hospital mortality by University HealthSystem Consortium expected in-hospital mortality

4. Invasive Support:

The following information will be recorded during the 12 hours prior to and 24 hours following ICU admission (“Time Zero”). If more than one value is available for this 36-hour period, the value closest to the time of ICU admission (“Time Zero”) will be recorded.

- a. Receipt of Mechanical Ventilation (Y/N)
- b. Receipt of vasopressors (Y/N) (norepinephrine, epinephrine, dopamine, phenylephrine, or vasopressin)

5. Renal function

- a. All serum creatinine values from the clinical laboratory system between 12 months prior to hospitalization and 30 days after ICU admission
- b. Stage II or greater acute kidney injury by KDIGO creatinine criteria

6. Serum laboratory values

- a. All serum values for sodium, potassium, chloride, bicarbonate, and blood urea nitrogen between 12 months prior to hospitalization and 30 days after ICU admission

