### **Final Anticipated Sample Size**

*(Protocol Amendment 3/29/17)*

As a cluster-randomized, multiple-crossover trial, SMART will enroll for a fixed duration, 82 unit-months over a calendar period of two years, and the total number of patients enrolled will depend on the rates of admissions to study ICUs during the fixed time period of the trial. The number of patients admitted to each of the participating ICUs has increased over the duration of the trial and we now anticipate at least 15,000 and no more than 16,500 patients will be enrolled during the planned study period.

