## Primary Outcome

The primary outcome will be the proportion of patients meeting one or more criteria for Major Adverse Kidney Events within the 30 days after enrollment (MAKE30): in-hospital mortality, receipt of new RRT, or persistent renal dysfunction defined as a final inpatient serum creatinine value  $\geq 200\%$  of baseline[22–24]. In-hospital mortality will be defined as death from any cause prior to hospital discharge censored at 30 days after ICU admission. Receipt of new RRT will be defined as receipt of any modality of RRT between ICU admission and the first of hospital discharge or 30 days, among patients not known to have received RRT prior to ICU admission. Persistent renal dysfunction will be defined as a final serum creatinine value before hospital discharge (censored at 30 days after enrollment)  $\geq 200\%$  of the baseline creatinine value. The value for baseline serum creatinine will be determined using a previously-described hierarchical approach[22]. The lowest serum creatinine between 12 months and 24 h prior to hospital admission will be used when available. If no such creatinine value is available, the lowest creatinine value between 24 h prior to hospital admission and the time of ICU admission will be used. If no creatinine value is available between 12 months prior to hospital admission and the time of ICU admission, a baseline creatinine value will be estimated using a previously-described formula [creatinine =  $0.74 - 0.2$  (if female) +  $0.08$  (if African American) +  $0.003 \times$  age (in years)][25]. Patients known to have received RRT prior to enrollment will be considered ineligible to meet criteria for new RRT or persistent renal dysfunction, but may qualify for MAKE30 by experiencing in-hospital mortality.

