### **Outcomes**

**Major Adverse Kidney Events within 30 days (MAKE30).** The MAKE30 composite outcome will be considered to have occurred when patients meet one or more of the following criteria in the 30 days after enrollment: (1) in-hospital mortality, (2) receipt of new renal replacement therapy (RRT), or (3) persistent renal dysfunction. Patients who

have received RRT prior to enrollment will be ineligible to meet the new RRT or persistent renal dysfunction criteria but will remain eligible to meet criteria for in-hospital mortality.

**In-hospital mortality** – In-hospital mortality will be defined as death from any cause prior to hospital discharge censored at 30 days after ICU admission (30-day in-hospital mortality).

**Receipt of new renal replacement therapy** – Receipt of new RRT will be defined as receipt of any modality of RRT between ICU admission and the first of (1) hospital discharge or (2) 30 days in a patient not known to have received RRT prior to ICU admission.

**Persistent renal dysfunction** – Persistent renal dysfunction will be defined as a final serum creatinine value before hospital discharge (censored at 30 days after enrollment) that is  $\geq$  200% of the baseline creatinine value.

**ICU-free days** – Intensive care unit-free days to day 28 (ICU-free days) will be defined as the number of days from the time of the patient's physical transfer out of the ICU until day 28 after enrollment. Patients who die prior to day 28 after enrollment will receive a value of 0 for ICU-free days. Patients who are never transferred out of the ICU prior to day 28 after enrollment will receive a value of 0 for ICU-free days. Patients who are transferred out of the ICU, return to the ICU, and are not subsequently transferred out of the ICU again before day 28 after enrollment will receive a value of 0 for ICU-free days. For patients who are transferred out of the ICU, are readmitted to the ICU, and are subsequently transferred out of the ICU again prior to day 28 after enrollment, ICU-free days will be awarded based on the time of the final transfer out of the ICU prior to day 28 after enrollment.

**Ventilator-free days** – Ventilator-free days to day 28 (VFDs) will be defined as the

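### As written, patients with RRT before enrollment can count as stage II or greater AKI, and incident AKI is not a subset of AKI

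*Combined protocol and SAP*

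**What the plan says.** SAP Appendix 2 (Renal Function) counts stage II or greater AKI when any creatinine from enrollment to the first of hospital discharge or day 30 is "at least 200% of the baseline value OR both (1) greater than 4.0 mg/dL and (2) increased at least 0.3 mg/dL from baseline". Incident AKI has its own rule. It needs a value at least 0.3 mg/dL above an earlier post-enrollment value, and that value must also be at least twice baseline, "at least 200% of a preceding post-enrollment value, or at least 4.0 mg/dL". The same paragraph presents AKI as either present at the first post-enrollment measurement or "acute kidney injury developing during the study (incident AKI". Neither rule mentions RRT before enrollment.

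For two other outcomes the SAP does address it. Under Primary Outcome: "Patients known to have received RRT prior to enrollment will be considered ineligible to meet criteria for new RRT or persistent renal dysfunction". Appendix 2 (Outcomes) repeats that patients who "have received RRT prior to enrollment will be ineligible to meet the new RRT or persistent renal dysfunction criteria". Persistent renal dysfunction is a final creatinine at or above 200% of the same baseline.

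Secondary Outcomes and Table 2 list AKI with no limit on the population. Table 2 places a row for AKI developing after enrollment directly below the AKI row. Age under 18 is the only exclusion (Protocol 6.0), so patients with earlier RRT are enrolled. They can be identified, because the data collected at enrollment include "Prior receipt of renal replacement therapy" (Protocol 8.4.1). Lower AKI incidence is one of four outcomes named in the secondary hypothesis (Protocol 1.0).

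**The concern.** Persistent renal dysfunction and the first limb of the AKI rule apply one threshold to one baseline. The first looks only at the final value, the second at any value. The plan therefore bars prior-RRT patients from the narrower creatinine outcome and leaves them eligible for the broader one. It draws the distinction elsewhere: subgroup g under Additional Secondary Analyses separates AKI from end-stage disease on RRT. That is a baseline category, though, and not a rule for the AKI outcome.

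Two things are at stake. Counting these patients in both arms adds events that say little about new kidney injury and so dilutes any difference. And if incident AKI is not contained in AKI, the Table 2 sub-row can hold patients who are absent from the row above it, so the two rows cannot be subtracted or read as part and whole.

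**Working it through.** The plan states no AKI rate, AKI sample size or prior-RRT share, so it has no figure to reproduce. The check is of the definitions, followed by an illustration of size.

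**1. The rules.** Let b be baseline, x a post-enrollment value and p an earlier post-enrollment value (mg/dL).

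- Overall AKI: x ≥ 2b, or (x > 4.0 and x − b ≥ 0.3).
- Incident AKI: x − p ≥ 0.3 and (x ≥ 2b, or x ≥ 2p, or x ≥ 4.0).

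**2. Creatinine paths.** The first four could occur in a patient with prior RRT; the last two need no RRT history.

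| b | Later values | Overall | Incident | Reason |
|---|---|---|---|---|
| 6.0 | 6.2, 5.0 | no | no | 6.2 − 6.0 = 0.2, and no later rise |
| 3.0 | 6.0 | yes | no | 6.0 = 2 × 3.0; only one value |
| 4.0 | 4.0, 5.5 | yes | yes | 5.5 > 4.0; rise of 1.5 from both references |
| 6.0 | 5.0, 5.8 | no | yes | 5.8 ≥ 4.0 and 0.8 above 5.0, yet below baseline |
| 1.5 | 0.7, 1.4 | no | yes | 1.4 = 2 × 0.7, yet below baseline |
| 3.6 | 3.6, 4.0 | no | yes | 4.0 meets ≥ 4.0 but not > 4.0 |

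So some prior-RRT patients qualify and some do not. Incident AKI escapes the overall rule in three ways: doubling from a post-enrollment value, ≥ 4.0 against > 4.0, and a 0.3 rise taken from a post-enrollment value instead of baseline.

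**3. No measured baseline.** Then "a baseline creatinine value will be estimated using a previously-described three-variable formula", with no exception for prior RRT. The lowest result is 0.74 − 0.2 + 0.003 × 18 = 0.594 (woman, 18). The highest is 0.74 + 0.08 + 0.003 × 90 = 1.09 (African American man, 90). Doubled, these are 1.19 and 2.18 mg/dL. One ICU value of about 1.2 to 2.2 or more is then AKI, even in a patient already on RRT.

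**4. Size (hypothetical).** From the documents: "at least 15,000 and no more than 16,500 patients will be enrolled during the planned study period" (Protocol 12.0), so N = 7,500 to 8,250 per arm; and a relative risk of 1 − 0.12 = 0.88, the planning value for MAKE30, borrowed here. Assumed: prior-RRT share f = 3 to 7%; share of them qualifying q = 25 to 50%; AKI rate in the rest a = 15 or 25%.

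- As written: fq + (1 − f)a against fq + (1 − f)0.88a, with N per arm.
- Prior RRT excluded: a against 0.88a, with N(1 − f) per arm.
- z = (p1 − p2)/√{[p1(1 − p1) + p2(1 − p2)]/n}; power = Φ(z − 1.96); information loss = 1 − (z as written / z excluded)².

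Extreme corner (f = 0.07, q = 0.5, a = 0.15, N = 7,500): saline 0.035 + 0.1395 = 0.1745; balanced 0.035 + 0.93 × 0.132 = 0.1578; relative risk 0.904. Here z is 2.76 as written and 3.06 with exclusion, so power is 78.7% against 86.3%.

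Mildest corner (f = 0.03, q = 0.25, a = 0.25): saline 0.0075 + 0.2425 = 0.2500; balanced 0.0075 + 0.97 × 0.22 = 0.2209; relative risk 0.884.

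| a | Change in saline AKI rate | Relative risk | Information loss | Power, excluded | Power, as written |
|---|---|---|---|---|---|
| 15% | +0.30 to +2.45 points | 0.886–0.904 | 4.8–18.7% | 86.3–90.5% | 78.7–89.1% |
| 25% | 0 to +1.75 points | 0.884–0.896 | 3.1–11.7% | 98.7–99.4% | 97.6–99.3% |

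If only 10 to 15% of prior-RRT patients qualify, the rate changes by 0 to −1.05 points, the relative risk is 0.882–0.888 and the loss 1.8–7.4%. The model ignores clustering and assumes no treatment effect in prior-RRT patients.

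**The case against.** The strongest reply is that little depends on this. The power calculation and stopping rule use MAKE30, death and new RRT, never AKI. The SAP section on multiple testing calls these secondary comparisons hypothesis-generating. The same rule applies in both arms. All of that stands and limits the point's weight.

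Second, the size rests on assumption. This also stands: the 7.7-point power drop is one corner of the grid, at 25% AKI the drop is about 1 point or less, and even the direction of change in the AKI rate depends on q.

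Third, the R code, cited in the SAP as Additional File 1, was not among the documents and may already filter these patients. That is possible. What can be shown is that the written rule admits them; if the code differs, the text is what needs correcting.

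Fourth, incident AKI has an explicit definition of its own, and a doubling from a post-enrollment low can fairly be called injury arising during the study. This stands as a reason not to force incident AKI to meet the overall rule. It does not rescue the presentation of incident AKI as a form of AKI, nor the mismatch at 4.0 mg/dL.

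A reader might infer that every patient on dialysis becomes an AKI case. The first path in the table shows otherwise. A reader might also infer that AKI rates must be inflated; that happens only if prior-RRT patients qualify more often than other patients.

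**Conclusion.** The point holds for the text as written. Some patients with RRT before enrollment meet the overall or incident AKI rule, although they are barred from the outcome that shares its threshold, and incident AKI is not nested in AKI. Both follow from the definitions without any assumption about frequency.

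The consequence is modest. It touches one secondary outcome, named in the secondary hypothesis but treated as hypothesis-generating. The expected direction is toward no difference, with a true relative risk of 0.88 appearing as roughly 0.88 to 0.90 under the assumed inputs. The actual size, and how often incident AKI occurs without AKI, cannot be estimated from the documents.

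It would be wrong to read this as a threat to the primary result: MAKE30 carries its own prior-RRT rule and is unaffected. Nor do the documents show bias in favour of either fluid. It should be fixed because the correction is cheap and the SAP aims at independent replication, which needs a settled numerator and denominator.

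**What to change.** In Appendix 2:

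- Apply the MAKE30 prior-RRT ineligibility rule to stage II or greater AKI, overall and incident, and report both among patients not known to have received RRT before enrollment.
- Use one inequality at 4.0 mg/dL in both rules.

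In Table 2, label the row for AKI developing after enrollment as a separately defined outcome, not a subset of the row above.

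If the R code already applies this filter, change the text to match it.

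The cost is two or three sentences, one row label and one filter on a variable already collected. There are two downsides. The AKI denominator becomes slightly smaller (by 3 to 7% under the assumed share). Genuine AKI is lost in patients whose earlier RRT was temporary, because the MAKE30 rule covers any known prior RRT; the text should say that this is intended.

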### **Outcomes**

**Major Adverse Kidney Events within 30 days (MAKE30).** The MAKE30 composite outcome will be considered to have occurred when patients meet one or more of the following criteria in the 30 days after enrollment: (1) in-hospital mortality, (2) receipt of new renal replacement therapy (RRT), or (3) persistent renal dysfunction. Patients who

have received RRT prior to enrollment will be ineligible to meet the new RRT or persistent renal dysfunction criteria but will remain eligible to meet criteria for in-hospital mortality.

**In-hospital mortality** – In-hospital mortality will be defined as death from any cause prior to hospital discharge censored at 30 days after ICU admission (30-day in-hospital mortality).

**Receipt of new renal replacement therapy** – Receipt of new RRT will be defined as receipt of any modality of RRT between ICU admission and the first of (1) hospital discharge or (2) 30 days in a patient not known to have received RRT prior to ICU admission.

**Persistent renal dysfunction** – Persistent renal dysfunction will be defined as a final serum creatinine value before hospital discharge (censored at 30 days after enrollment) that is  $\geq$  200% of the baseline creatinine value.

**ICU-free days** – Intensive care unit-free days to day 28 (ICU-free days) will be defined as the number of days from the time of the patient's physical transfer out of the ICU until day 28 after enrollment. Patients who die prior to day 28 after enrollment will receive a value of 0 for ICU-free days. Patients who are never transferred out of the ICU prior to day 28 after enrollment will receive a value of 0 for ICU-free days. Patients who are transferred out of the ICU, return to the ICU, and are not subsequently transferred out of the ICU again before day 28 after enrollment will receive a value of 0 for ICU-free days. For patients who are transferred out of the ICU, are readmitted to the ICU, and are subsequently transferred out of the ICU again prior to day 28 after enrollment, ICU-free days will be awarded based on the time of the final transfer out of the ICU prior to day 28 after enrollment.

**Ventilator-free days** – Ventilator-free days to day 28 (VFDs) will be defined as the

number of days from the time of initiating unassisted breathing until day 28 after enrollment. Patients who die prior to day 28 after enrollment will receive a value of 0 for VFDs. Patients who never achieve unassisted breathing prior to day 28 after enrollment will receive a value of 0 for VFDs. Patients who achieve unassisted breathing, return to assisted breathing, and do not again achieve unassisted breathing before day 28 after enrollment will receive a value of 0 for VFDs. For patients who achieve unassisted breathing, return to assisted breathing, and subsequently achieve unassisted breathing again prior to day 28 after enrollment, VFDs will be awarded based on the time of the final initiation of unassisted breathing prior to day 28 after enrollment. Survivors who never experience assisted breathing will receive 28 VFDs.

**Vasopressor-free days** – Vasopressor-free days to day 28 will be defined as the number of days from the time of vasopressor cessation until day 28 after enrollment. Patients who die prior to day 28 after enrollment will receive a value of 0 for vasopressor-free days. Patients who never cease to receive vasopressors prior to day 28 after enrollment will receive a value of 0 for vasopressor-free days. Patients who achieve vasopressor cessation, return to receiving vasopressors, and do not again achieve vasopressor cessation before day 28 after enrollment will receive a value of 0 for vasopressor-free days. For patients who achieve vasopressor cessation, return to receiving vasopressors, and subsequently achieve cessation of vasopressors again prior to day 28 after enrollment, vasopressor-free days will be awarded based on the time of the final cessation of vasopressors prior to day 28 after enrollment. Survivors who never receive vasopressors will receive 28 vasopressor-free days.

**Renal replacement therapy-free days** – Renal replacement therapy-free days to day 28 (RRT-free days) will be defined as the number of days from the time the final RRT treatment until day 28 after enrollment. Patients who die prior to day 28 after enrollment will receive a value of 0 for RRT-free days. Patients who continue to receive RRT through day 28 after enrollment will receive a value of 0 for RRT-free days. Patients who achieve RRT cessation, return to receiving RRT, and do not again achieve RRT cessation before day 28 after enrollment will receive a value of 0 for RRT-free days.

For patients who achieve RRT cessation, return to receiving RRT, and subsequently achieve cessation of RRT again prior to day 28 after enrollment, RRT-free days will be awarded based on the time of the final RRT treatment prior to day 28 after enrollment. Survivors who never receive RRT will receive 28 RRT-free days.

